- i) **Clinical Data** – All clinical data (weights, laboratory results, imaging results) will be stored in the patient's electronic medical record
- ii) **Adverse Events** – All adverse events reported by parents or noted by physicians will be recorded in the patient's medical record. They will also be reported to the IRB following a pre-determined schedule (see Data Safety Monitoring Plan in appendix)

F. Statistical Considerations

- i) **Overview**

This is a Phase 2 clinical trial using the two-stage "minimax" design described by Simon.¹³ As a Phase 2 trial, the trial's objective is to determine whether PTX has sufficient biological activity against BA to warrant further study. By choosing the two-stage "minimax" design, we gain two advantages: (i) early termination if the drug is not efficacious, and (ii) an overall smaller sample size to test the hypothesis. One limitation is that the design identifies only large effects (response >20%). For BA this is appropriate, because the field is in need of a robust therapy that can substantially limit liver damage and delay/prevent need for LT.

The Phase 2 design involves administering PTX to all subjects and comparing their response to historical controls. Hence, the study has no randomization or control arm. Historical controls from BA patients seen at Texas Children's hospital between 2006-2010 will be used. Of those receiving the KP (equivalent to Group 1 study subjects), 21/36 or 58.3% had normal CB levels 3 months post-KP. This agrees with previously published figures from other centers.¹⁵ Of those not receiving the KP (equivalent to Group 2 study subjects), 1/13 or 7.7% had stable CB levels after 3 months.

Historical controls in this study are appropriate for a number of reasons. The same two pediatric surgeons performing all of the KPs in the past will perform the KPs for future study subjects. Furthermore, neither the KP surgical technique nor our medical management of patients with BA has changed over the years. Rather, the only difference is that the number of patients with BA seen at Texas Children's Hospital has increased. One potential bias that may arise is that we may be more vigilant to ensure study subjects take PTX, which may lead to more overall care. To control for this, we will adhere to the same clinic schedule and guidelines as we have used in the past.

In this study, Group 1 and Group 2 patients will be analyzed independently:

[figure not shown]

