- Group 1) Infants receiving the KP will be given PTX for 12 weeks, and the number whose CB levels return to normal (0.0-0.3 mg/dL) will be calculated. Historically, as mentioned above, ~60% of such infants have normal CB levels after 12 weeks. The study will determine whether PTX improves this percentage.
- Group 2) Infants not receiving the KP will be given PTX for 12 weeks, and the number whose CB levels stabilize (within 10% of starting level) will be calculated. Historically, as mentioned above, ~10% of such infants have stable CB levels after 12 weeks. The study will determine whether PTX improves this percentage.

ii) Sample-Size Calculations

For sample size calculations, we use previously-derived tables for the "minimax" design for two-stage studies described by Simon.¹³ Because BA is in need of a robust therapy, we designed the study to detect a large effect (>20% increase in responders). We used standard values for significance (alpha = 0.05) and power (beta = 0.2). Our total sample size is the sum of patients needed in Groups 1 and 2 (35 and 25, respectively).

For Group 1, approximately 60% of patients receiving the KP have a normal CB (0.0-0.3 mg/dL) 12 weeks later based on historical data (null hypothesis). We are interested in determining whether PTX can increase this to 80% of patients (alternative hypothesis), which would be a large enough response to make the medication worth pursuing in a larger Phase 3 trial. To test the null hypothesis versus the alternative hypothesis at a significance level of 0.05 and power of 80%, 35 patients must be enrolled. Of these 35, 26 or more patients must respond to reject the null hypothesis. Furthermore, the study will be terminated early if, of the first 13 patients, fewer than 9 respond.

For Group 2, approximately 10% of patients not receiving a KP have a stable CB (within 10% of the starting CB) 12 weeks after diagnosis based on historical data (null hypothesis). We are interested in determining whether PTX can increase this to 30% of patients (alternative hypothesis), which would be a large enough response to make the medication worth pursuing in a larger Phase 3 trial. To test the null hypothesis versus the alternative hypothesis at a significance level of 0.05 and power of 80%, 25 patients must be enrolled. Of these 25, 6 or more patients must respond to reject the null hypothesis. Furthermore, the study will be terminated early if, of the first 15 patients, fewer than 2 respond.

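### Cheap improvement, mainly for Group 1: close enrolment once a positive result is arithmetically out of reach; alpha and power stay exactly the same

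*Combined protocol and SAP*

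**What the plan says.** Section F.ii sets up a separate two-stage minimax design for each group.

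- **Group 1 (KP):** null rate 60%, alternative 80%; "at a significance level of 0.05 and power of 80%, 35 patients must be enrolled". At the first stage, "the study will be terminated early if, of the first 13 patients, fewer than 9 respond". At the end, "Of these 35, 26 or more patients must respond to reject the null hypothesis".
- **Group 2 (no KP):** null rate 10%, alternative 30%, 25 infants, at least 6 responders needed. At the first stage, "the study will be terminated early if, of the first 15 patients, fewer than 2 respond".

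F.ii has no rule between the first-stage look and the final count.

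Section III (Stopping Rules) of the Data Safety Monitoring Plan restates the first-stage looks, adds stops for a positive outcome, and adds a stop for multiple unanticipated serious adverse events. It has no futility stop after infant 13 or 15. Its first-stage rules count non-responders where F.ii counts responders: 9 non-responders of 13 in Group 1 and 2 of 15 in Group 2. F.ii implies 5 and 14.

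Sections B and F.i both give early termination of an ineffective drug as the first advantage of the design.

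**The concern.** Each infant's response is known 12 weeks after starting PTX, and infants enter one at a time. A group can therefore reach a point where no further run of responses can produce a positive result, while F.ii lets enrolment continue to 13 or 35 (Group 1) or to 15 or 25 (Group 2). Infants enrolled after that point take an investigational drug, and are barred from other experimental therapies meanwhile, in a group whose primary conclusion is already settled. At stake are a few infants and some calendar time. The validity of the test is not at stake.

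**Working it through.** **Inputs.** From F.ii: Group 1 n1 = 13, continue if at least 9 respond, n = 35, succeed if at least 26 respond, p0 = 0.60, p1 = 0.80. Group 2: n1 = 15, at least 2; n = 25, at least 6; p0 = 0.10, p1 = 0.30. From F.i: 36 KP and 13 no-KP infants seen in 2006-2010. From F.i and F.ii: 12 weeks to outcome. F.ii does not say whether alpha is one- or two-sided; the one-sided exact binomial reproduces the design.

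**1. The plan's own figures.** For Group 1 the probability of rejection at rate p is the sum over x = 9 to 13 of P(Bin(13,p) = x) × P(Bin(22,p) ≥ 26 − x); Group 2 is analogous.

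- Group 1: alpha 0.0499, power 0.808. Stage 1 stop under the null: P(Bin(13, 0.6) ≤ 8) = 0.647. Expected N = 13 + 0.353 × 22 = 20.77.
- Group 2: alpha 0.0328, power 0.802. Stage 1 stop under the null: P(Bin(15, 0.1) ≤ 1) = 0.549. Expected N = 15 + 0.451 × 10 = 19.51.

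A full search for the minimax design at alpha 0.05 and power 0.80 returns exactly the plan's boundaries in both groups.

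**2. Where success becomes impossible.** The number of non-responders that rules out a threshold is (size − required responders + 1).

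- Group 1: 13 − 9 + 1 = 5 within the first 13; 35 − 26 + 1 = 10 overall.
- Group 2: 15 − 2 + 1 = 14 within the first 15; 25 − 6 + 1 = 20 overall.

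**3. Effect on alpha and power.** Closing there removes only paths that already end in non-rejection, so the rejection probability is the same at every true rate. An exact recursion over (infants evaluated, responders) confirms 0.0499/0.808 and 0.0328/0.802. The 12-week lag does not alter this.

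**4. Saving with no lag (upper bound).**

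| | Expected N, plan | Expected N, closing early | Saving |
|---|---|---|---|
| Group 1, null (60%) | 20.77 | 16.69 | 4.07 |
| Group 1, alternative (80%) | 32.82 | 32.31 | 0.51 |
| Group 2, null (10%) | 19.51 | 18.51 | 1.00 |
| Group 2, alternative (30%) | 24.65 | 24.52 | 0.13 |

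(Savings are taken before rounding.) Under the null, 29% of Group 1 trials pass stage 1 and then become unable to succeed before infant 35, on average at infant 27.8.

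**5. Saving with the lag.** The documents give no accrual rate for the trial. Assuming five full years of historical intake and that every infant enrols, 36/5 = 7.2 a year (Group 1) and 13/5 = 2.6 a year (Group 2). About 7.2 × 12/52 = 1.7 Group 1 infants are then pending at any time. Simulated with Poisson arrivals under the null:

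- Group 1, enrolment paused at the look: 20.7 to 17.9, saving 2.8 (14%).
- Group 1, no pause: 21.8 to 18.2, saving 3.6 (17%).
- Group 2: 19.5 to 18.8 with a pause and 19.9 to 19.1 without, saving 0.7 to 0.8.
- Group 1 at a doubled rate (14.4 a year), with a pause: saving about 1.8.

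A simpler model with a fixed number of infants pending and a pause at the look gives Group 1 savings of 3.2 (1 pending), 2.5 (2), 1.9 (3), 1.0 (5) and 0.3 (8). Group 2 gives 0.4 (1), 0.1 (2) and 0 (3 or more).

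**6. Effect on the raw response rate.** With a true Group 1 rate of 60%, the mean observed proportion is 56.8% under the plan and 53.5% with early closing. The bias goes from −3.2 to −6.5 points.

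**The case against.** A single futility look is the standard form of Simon's design, the boundaries are right, and the promised early termination is delivered: an inactive drug stops at stage 1 with probability 0.647 in Group 1 and 0.549 in Group 2. The gain shrinks with the lag and with faster accrual, and F.i itself says patient numbers have grown. It is negligible if PTX works. Early closing also leaves fewer infants for the descriptive outcomes of Objective 2 and makes the raw response rate more biased. All of this stands. It limits the size of the point but does not remove it, because the saving costs nothing in alpha or power.

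Three stronger readings are tempting, and the documents do not support them.

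- *The sample-size design is faulty.* It is not; the stated boundaries reproduce exactly.
- *Enrolment is bound to continue to 13, 35, 15 or 25.* That follows from F.ii alone. Read literally, the Stopping Rules would close Group 2 at its 2nd non-responder, long before F.ii would. What can be said is that F.ii permits futile enrolment, and that the two sections conflict.
- *Group 1 would shrink by 20%, from 20.8 to 16.7 infants.* That requires each outcome to be known before the next infant enters, which a 12-week outcome rules out at any realistic accrual.

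**Conclusion.** The point holds as a cheap improvement, chiefly for Group 1 when PTX is inactive. There the expected saving is about 3 to 3.6 infants at 7.2 a year, bounded above by 4.1 with no lag and falling to about 1.8 if accrual doubles and enrolment pauses at the look. Group 2 saves fewer than 1 infant. If PTX works, the saving is at most 0.5 (Group 1) and 0.13 (Group 2). That alpha and power are unchanged is exact and needs no assumption about accrual. The size of the saving rests on the assumed accrual rate and on whether enrolment pauses at the first look, which the documents do not say.

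**What to change.** Add to F.ii, and carry in the same terms into the Stopping Rules of the Data Safety Monitoring Plan:

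> Enrolment in Group 1 closes once 5 of the first 13 infants, or 10 in total, are week-12 non-responders. Enrolment in Group 2 closes once 14 of the first 15, or 20 in total, are week-12 non-responders. The null hypothesis for that group is then not rejected.

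The final thresholds of F.ii stay as they are. The rule governs enrolment only and says nothing about the treatment of infants already enrolled.

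Three things should go with it:

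1. Reconcile the conflicting first-stage counts in F.ii and the Stopping Rules. The counts above follow from F.ii; if its thresholds change, recompute them.
2. State how an infant without a week-12 bilirubin is classified, in the running count and in the final analysis alike, since one more non-responder can close a group.
3. Report the response rate after early closure with an estimate that accounts for the stopping rule, not the raw proportion alone.

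The cost is a short addition in two places, a running count of a result already measured at week 12, and fewer infants for the descriptive outcomes in a group that can no longer succeed.

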Schedule of AE reporting (all on a subject-by-subject basis)

Grade 1-4 AEs typically seen in BA	Report after 12 weeks of therapy to IRB
Grade 1-4 AEs not typically seen in BA	Report within 14 days to IRB

All Grade 5 AEs	Report within 7 days to IRB
All subjects withdrawing from study	Report within 7 days to IRB
Other unintended protocol deviations	Report within 14 days to IRB

III. Stopping Rules

1. In Group 1, the study will be terminated if 9 of the first 13 subjects do not respond to PTX therapy (negative outcome).
2. In Group 1, the study will be terminated if the first 26 subjects do respond (positive outcome).
3. In Group 2, the study will be terminated if 2 of the first 15 subjects do not respond to PTX therapy (negative outcome).
4. In Group 2, the study will be terminated if the first 6 subjects do respond (positive outcome).
5. In both groups, the study will be terminated if multiple unanticipated serious AEs occur from PTX therapy. This decision will be made in conjunction with the IRB.

CONSENT FORM

Institutional Review Board for Baylor College of Medicine and Affiliated Hospitals Pentoxifylline in Biliary Atresia

H-31387 - PENTOXIFYLLINE THERAPY IN BILIARY ATRESIA

Background

You are invited to take part in a research study, to determine whether the medication PENTOXIFYLLINE reduces liver damage in BILIARY ATRESIA.

Please read this information and feel free to ask any questions before you agree to take part in the study.

WHAT IS BILIARY ATRESIA?

Biliary atresia is a serious liver disease that affects infants. Approximately 1 in every 10,000 infants has the disease. We do not know why some infants have the disease while others do not.

Biliary atresia occurs when narrow tubes called bile ducts become blocked. Normally, the liver sends liquids to the intestines through bile ducts. One liquid the liver sends is called bile. Bile is a strong chemical that digests the fats we eat.

In biliary atresia, the bile duct becomes blocked. Bile can no longer pass through to the intestines. Instead, bile stays in the liver. Bile starts digesting the liver and over time causes liver damage.

In order to live, we need our liver to work properly. In biliary atresia, the liver becomes damaged and stops working properly. Biliary atresia causes death if it is not treated.

HOW IS BILIARY ATRESIA TREATED?

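### The futility rules in the Data Safety Monitoring Plan count non-responders where Section F.ii counts responders; followed as written, they would stop Group 2 almost surely even if PTX works

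*Combined protocol and SAP*

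**What the plan says.** Section F.i describes a Simon two-stage minimax design, with Groups 1 and 2 analysed independently. Section F.ii sets the error rates: "We used standard values for significance (alpha = 0.05) and power (beta = 0.2".

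For futility, F.ii says of Group 1 that "the study will be terminated early if, of the first 13 patients, fewer than 9 respond", and of Group 2 that "the study will be terminated early if, of the first 15 patients, fewer than 2 respond". Its final success criteria are at least 26 responders of 35 and at least 6 of 25.

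The Data Safety Monitoring Plan (Appendix J.i, part III, Stopping Rules) gives a different set:

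- Rule 1: "In Group 1, the study will be terminated if 9 of the first 13 subjects do not respond to PTX therapy (negative outcome".
- Rule 2, for Group 1: "the study will be terminated if the first 26 subjects do respond (positive outcome".
- Rule 3: "In Group 2, the study will be terminated if 2 of the first 15 subjects do not respond to PTX therapy (negative outcome".
- Rule 4, for Group 2: "the study will be terminated if the first 6 subjects do respond (positive outcome".

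**The concern.** The two sections use the same pairs of numbers, 9 of 13 and 2 of 15, but one counts responders and the other counts infants who do not respond. These are different decision rules, and both stand in the current text.

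Rule 3 also conflicts with the trial's own success criterion. Six responders of 25 leaves room for 19 non-responders, whereas rule 3 ends the group at two. If PTX met its 30% target, about 15 × 0.70 = 10.5 of the first 15 infants would be non-responders, so a drug performing exactly as hoped would be declared negative.

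Rule 1 errs the other way. It makes the Group 1 futility look so lenient that it almost never stops an ineffective drug. Sections B and F.i give early termination for lack of efficacy as one of the design's two advantages.

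Rules 2 and 4 add stops for a positive result, which F.ii does not have, and it is unclear whether they mean an unbroken run of responders or a cumulative count.

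**Working it through.** **Inputs, all from Section F.ii**

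| | Group 1 | Group 2 |
|---|---|---|
| Null rate p0 | 0.60 | 0.10 |
| Target rate p1 | 0.80 | 0.30 |
| Stage 1 size n1 | 13 | 15 |
| Total N | 35 | 25 |
| Success if responders ≥ | 26 | 6 |
| F.ii stops if stage 1 responders ≤ | 8 | 1 |

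**The DSMP rules in responders.** Reading the rules as at least 9, or at least 2, non-responders:

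- Group 1 stops if responders ≤ 13 − 9 = 4.
- Group 2 stops if responders ≤ 15 − 2 = 13.

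**Formulas.** X1 is the number of responders among the first n1 infants, X2 the number among the remaining N − n1, c the largest X1 that stops the group, and R the final criterion.

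- P(early stop) = P(X1 ≤ c), with X1 ~ Binomial(n1, p)
- P(success) = Σ over x > c of P(X1 = x) · P(X2 ≥ R − x), with X2 ~ Binomial(N − n1, p)
- Expected N = n1 + (N − n1) · [1 − P(early stop)]

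P(success) is the type I error at p0 and the power at p1.

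**Step 1: reproduce F.ii**

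| | Group 1 | Group 2 |
|---|---|---|
| P(early stop) at p0 | 0.647 | 0.549 |
| P(early stop) at p1 | 0.099 | 0.035 |
| Type I error | 0.0499 | 0.0328 |
| Power | 0.808 | 0.802 |
| Expected N at p0 | 20.8 | 19.5 |

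Both groups meet alpha 0.05 and 80% power. An exhaustive search found no qualifying design at N = 33 or 34 (60% versus 80%) or at N = 23 or 24 (10% versus 30%). At N = 35 and N = 25, the designs with the lowest expected N under the null are 8/13, 25/35 and 1/15, 5/25. These are F.ii's thresholds.

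**Step 2: Group 2 under DSMP rule 3, same final criterion**

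At p = 0.30, P(X1 ≥ 14) = 15 × 0.30^14 × 0.70 + 0.30^15 = 5.02 × 10⁻⁷ + 0.14 × 10⁻⁷ = 5.2 × 10⁻⁷.

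So P(stop) = 0.9999995. Any group that continues already has at least 14 responders, so power equals the chance of continuing, about 0.0000005 against 0.802.

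| True response rate | P(stop), F.ii | P(stop), DSMP |
|---|---|---|
| 30% | 0.035 | 0.9999995 |
| 50% | 0.0005 | 0.9995 |
| 80% | <0.0001 | 0.833 |

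The second non-responder can occur before infant 15, so the stop comes by infant 15 rather than necessarily at it.

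**Step 3: Group 1 under DSMP rule 1, same final criterion**

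| | F.ii | DSMP |
|---|---|---|
| P(early stop) at 60% | 0.647 | 0.032 |
| Expected N at 60% | 13 + 22 × 0.353 = 20.8 | 13 + 22 × 0.968 = 34.3 |
| Type I error at 60% | 0.0499 | 0.0575 |
| Power at 80% | 0.808 | 0.854 |

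A single-stage test of at least 26 of 35 also has type I error 0.0575, so rule 1 leaves the interim look with practically no effect.

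**Step 4: the positive rules**

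- Read as unbroken runs: 0.80^26 = 0.003 and 0.30^6 = 0.0007 at the target rates. They almost never apply and do not rescue Group 2.
- Read as stopping at the sixth responder in Group 2, with F.ii's futility rule and a true rate of 30%: power stays at 0.802, but the mean estimated response rate among positive trials is 37%, against 33% when all 25 infants are observed.

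**The case against.** The strongest reply is that rules 1 and 3 can be read with the negation covering the whole clause: stop unless 9 of the first 13 respond, or unless 2 of the first 15 respond. That reading equals F.ii, and the matching numbers and the negative-outcome label support it. F.ii is itself an instruction to stop, it is clear, and a team following it would do no harm. The supporting evidence makes a drafting slip likely. It does not make the text safe: counting non-responders is the plain reading, no precedence between the sections is stated, and the DSMP gives monitoring to the investigators without describing an independent board that might catch the error.

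Four qualifications stand:

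- The Group 1 type I error excess is small (0.0575 − 0.05 = 0.0075) and arises at the design null of 60%. At the unrounded historical rate, 21/36 = 58.3%, the DSMP rule gives 0.038. The larger Group 1 loss is the futility look.
- Read as cumulative counts, rules 2 and 4 are curtailment. Once 26 or 6 responders are reached, success under F.ii is already assured, so with F.ii's futility rules alpha and power are unchanged. What remains is unclear wording, fewer infants observed, and upward bias in a response estimate that Section F does not formally plan.
- The figures assume at least 9 or at least 2 non-responders. With exactly 2, Group 2 would almost never stop (probability 0.000008 at 30%), which is no futility rule and still contradicts F.ii. Group 1's type I error would remain 0.0575.
- F.ii's own arithmetic is correct. The fault is an inconsistency between sections.

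**Conclusion.** The concern holds. On their plain reading, DSMP rules 1 and 3 invert the F.ii futility rules. Group 2 is the serious case: at the 30% target it would stop by infant 15 with probability above 0.99999, leaving power of about zero in place of 0.802. In Group 1 the futility look is nearly lost (0.647 to 0.032 at the null), about 34.3 − 20.8 = 13.5 more infants would be expected to be enrolled on an ineffective drug, and type I error is 0.0575 at the 60% design null.

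These figures assume independent responses with a common rate in each group, F.ii's final criteria, and a team that follows the DSMP. Only the F.ii futility thresholds reproduce the stated design. This must be fixed, because the rule as written could produce a wrong conclusion about the drug.

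**What to change.** Amend part III of the DSMP:

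- Rule 1: stop enrolment to Group 1 if 8 or fewer of the first 13 infants respond.
- Rule 3: stop enrolment to Group 2 if 1 or fewer of the first 15 infants respond.
- Rules 2 and 4: delete them, or replace them with the F.ii final criteria (at least 26 of 35; at least 6 of 25). If stopping once the criterion is reached is really intended, state it as a cumulative count in both F.ii and the DSMP, and say how the response rate will be estimated.
- In all four, refer to enrolment in that group instead of the study, since F.i analyses the groups independently.

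The cost is a wording amendment to four lines. Sample size, procedures and the F.ii calculations do not change.
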